#### 10.1.2. *Serious Adverse Event*

An AE is **serious** when the patient outcome is one or more of the following:

- Death.
- Life-threatening, meaning that the patient was at immediate risk of death from the event at the time that the event occurred. It does not include an event which hypothetically might have caused death if it occurred in a more severe form.
- Hospitalization, initial or prolonged, meaning that a hospital admission and/or prolongation of a hospital stay was required for the treatment of the AE, or occurred as a consequence of the event. It does not include a pre-planned elective hospital admission for treatment or diagnostic procedures, or, in general, a hospital admission of less than 24 hours duration.
- Disability or incapacity that is persistent or significant.

---

 A medical product may be a drug or a device being used either prior to or after regulatory approval. The medical product in this protocol will hereafter be referred to as study drug (synonym: investigational agent).

- Congenital anomaly or birth defect.
- Important medical event that, although not immediately life-threatening, requires intervention in order to prevent one of the other serious outcomes listed above. Examples of such events are allergic bronchospasm requiring intensive treatment in an emergency room or at home; blood dyscrasias or convulsions that do not result in hospitalization; or the development of drug dependency or drug abuse.

#### **10.1.3. *Suspected Unexpected Serious Adverse Reaction (SUSAR)***

A SUSAR is defined as an SAE that meets **both** the following criteria with respect to study drug:

- *Suspected* — is assessed as related or possibly related to study drug (see [Section 10.4.3](#));
- *Unexpected* — compared to the study drug-related AEs described in Investigator's Brochure, the event meets **any** of the following criteria:
  - The event was not previously described;
  - The event is now characterized as more severe (see [Section 10.4.4](#));
  - The event is now characterized more specifically (e.g., an event of "interstitial nephritis" in a patient receiving an agent previously described as associated with "acute renal failure").

In clinical trials involving ill patients, events considered related to the natural history of the disease under study or to lack of efficacy (that is, the event is considered more likely related to those factors than to other factors, including study drug) are not considered "unexpected." Lack of efficacy is recorded as specified elsewhere in the Protocol.

#### **10.2. *Investigator Assessment of Safety Laboratory Tests***

The Investigator will review the results of all Safety Laboratory tests (see [Section 9.7.2](#)) and designate any results outside of the reference range as **either** of the following:

- Abnormal, not clinically significant (NCS).
- Abnormal, clinically significant (CS).

In making this judgment, the Investigator will consider all available information, including the patient's clinical condition, all available laboratory results (central and local), and the potential for false positive test results. In addition, laboratory studies that result in the actions specified in [Section 10.1.1](#) will be classified as CS.

Any result assessed as CS will be recorded as an AE *unless* it is consistent with one or more of the following:

- Process noted in the medical history.
- Ongoing AE already recorded.
- Expected course of the primary disease under study.

### 10.3. Recording Adverse Events

Procedures for the collection and recording of AEs are as follows:

- From obtaining informed consent through EOS, there will be active surveillance to identify all AEs. Events will be recorded in the AE portion of the EDC, with particular attention to whether the onset of the event was before or after the administration of the first dose of study drug. All recorded events will be included in applicable line listings, but only events with onset after administration of the first dose will be included in summaries of TEAEs (see [Section 12.2](#)).
- After the EOS, surveillance will be passive (only events brought to the Investigator's attention will be considered) and only events assessed as SUSARs will be recorded (see [Section 10.1.3](#)).
- In accordance with the FDA guidance document – Safety Reporting Requirements for Investigational New Drugs (INDs) and Bioavailability/Bioequivalence (BA/BE) Studies – disease progression does not require reporting as an AE or SAE. However, signs and symptoms related to disease may be reported at the discretion of the Investigator.

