#### ***6.5.4. Procedures for Assessment of Patients with Changes in Complement Levels***

Activation of complement in non-human primates is a well-described effect of phosphorothioate oligonucleotides, including IMO-8400. Monkeys are thought to be particularly sensitive to oligonucleotide-induced complement activation and a similar direct oligonucleotide-induced complement activation has not been observed in humans or other species. Specifically, in a 39 week chronic toxicity study conducted in cynomolgus monkeys, 3 of 28 animals administered IMO-8400 at dose levels  $\geq$  6 mg/kg/week were found dead or sacrificed moribund during the study with necropsy findings of myocardial degeneration/necrosis, glomerulonephritis, and/or hepatocellular necrosis. These findings correlated with changes in serum complement levels. Alterations in serum complement in these animals were noted in the weeks to months preceding their unscheduled deaths.

If at any time during study participation, a patient experiences an acute drop in complement (50% hemolytic complement assay [CH50], complement component 3 [C3], or complement component 4 [C4]) levels  $\geq$  50% or a drop to an absolute value below the lower limit of normal with reference to baseline testing or most recent values on study, the following procedures and testing should be performed:

1. Hold study drug treatment
2. Repeat the serum complement test to confirm decreased complement levels
3. Query patient for recent change in signs or symptoms suggestive of a rheumatologic or vasculitic event, i.e. recent appearance of a rash or bruising, new onset symptoms such as fever, arthralgias, or fatigue
4. Perform physical examination with careful attention to findings suggestive of vasculitis; i.e., rash, palpable purpura, petechiae
5. Perform repeat complete blood count (CBC) with platelets, or review most recent CBC/platelets
6. Perform repeat urinalysis, or review most recent urinalysis with special attention to findings suggestive of glomerulonephritis; i.e., presence of protein, blood, red blood cell casts or white blood cell casts
7. Perform an ECG

Based on the results of this work-up and the patient's disease assessment/response to study drug, the Investigator in discussion with the Sponsor's medical monitor, will determine the patient's risk/benefit profile and discuss appropriate next steps regarding the patient's continued participation in the study.

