### **6.10.2.2. Duration of Treatment**

Treatment with IMO-8400 will continue until study completion or until the patient experiences intolerable toxicity, disease progression, or withdraws consent, whichever comes first.

**Follow-Up.** Additionally, patients who have discontinued study treatment for reasons other than progressive disease will be assessed per Response Assessment in WM from the VIth International Workshop, at a minimum of every 12 weeks ( $\pm$  4 weeks) until documentation of progressive disease, start of new anti-cancer therapy, or until study completion, for up to 6 months from the last patient's first treatment (Cycle 1, Day 1), whichever comes first.

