#### **10.4.8. Follow-up and Outcome of AEs**

If possible, AEs will be followed until resolved (synonyms: recovered, recuperated, ended) either with or without sequelae, including for patients who prematurely discontinue study participation. For AEs that are assessed as not drug-related and are not resolved at the EOS visit, follow-up may be limited with the approval of the Medical Monitor.

The outcome of each event will be described using the following categories:

- **Resolved without sequelae** — the event resolved and patient returned to baseline.
- **Resolved with sequelae** — the event resolved but the patient is left with residual problems (e.g., functional deficits, pain).
- **Resolving** — at the last observation, the event was improving.
- **Not Resolved** — at the last observation, the event was unchanged.
- **Death (Fatal)** — to be used for the *one* AE which, in the judgment of the Investigator, was the *primary* cause of death.
- **Unknown** — there were no observations after the onset (initial observation or report) of the event.

Note: Resolving and Not Resolved may also be used for AEs that were unresolved at the time a patient died, but were *not* assessed as the primary cause of death.

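### After the End-of-Study visit, late drug-related serious events that match the Investigator's Brochure are not recorded, and section 10.3 does not fit section 10.5.2

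*Protocol*

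**What the plan says.** Protocol section 10.3 divides adverse event recording into two periods.

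- **Up to EOS:** "From obtaining informed consent through EOS, there will be active surveillance to identify all AEs". Section 1.4 places the EOS visit 30 to 35 days after the last dose.
- **After EOS:** surveillance is passive, meaning that "only events brought to the Investigator's attention will be considered", "and only events assessed as SUSARs will be recorded".

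Section 10.1.3 defines a SUSAR as an SAE that meets two conditions. It is suspected, that is, it "is assessed as related or possibly related to study drug". It is also unexpected against the drug-related events in the Investigator's Brochure. Any one of three tests makes it unexpected: "The event was not previously described", or it is now more severe than described, or it is now characterized more specifically.

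Three other places bear on the point:

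- The schedule of events (Table 4) runs AE monitoring from Screening to the EOS visit.
- Section 6.10.2.2 provides that "patients who have discontinued study treatment for reasons other than progressive disease will be assessed per Response Assessment in WM" at least every 12 weeks (± 4 weeks). This continues until progression, new anti-cancer therapy or study completion, for up to 6 months from the last patient's first treatment.
- Section 10.5.2 requires initial notification of each SAE within 24 hours of the Investigator becoming aware of it, and gives no end date.

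**The concern.** Expectedness has a proper use in section 10.5.4, where it decides which events go rapidly to regulators and IRBs. In section 10.3 it also decides whether a late event enters the trial's data at all. These are different purposes. An expected drug-related SAE may need no expedited report, but it is still part of the drug's safety profile.

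Safety and tolerability are the primary objective (section 5.1). Section 12.3 tabulates treatment-emergent events by dose level, intensity and relationship. Section 10.3 admits to those summaries events with onset after the first dose and states no closing date. As written, a late related SAE that is new to the Brochure can reach the tables, while one that the Brochure already describes cannot. The gap is thus not a random loss of late events. It falls on the reactions already attributed to the drug.

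The second difficulty is practical. A site that reads section 10.5.2 would notify a late, expected, related SAE. A site that reads section 10.3 would not record it. Two sites could handle the same event differently and both believe that they had complied.

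**Working it through.** No figure in the protocol is at stake, so the check sets the recording rule against the definition that it relies on.

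**Step 1. Apply 10.1.3 to the post-EOS rule in 10.3.** Take an event that comes to the Investigator's attention:

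| Onset | Event | SUSAR under 10.1.3? | Recorded under 10.3? |
|---|---|---|---|
| Up to EOS | Any AE | not needed | Yes |
| After EOS | SAE, not suspected | No | No |
| After EOS | Related or possibly related SAE, not in the Brochure | Yes | Yes |
| After EOS | Related or possibly related SAE, listed, but now more severe | Yes | Yes |
| After EOS | Related or possibly related SAE, listed, but now more specific | Yes | Yes |
| After EOS | Related or possibly related SAE, listed, same kind, severity and specificity | No | **No** |

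The last row is the gap. Suspected SAEs after EOS split into unexpected (recorded) and expected (not recorded).

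**Step 2. Look for a passage that restores the last row.**

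- Table 4 does not, because its AE monitoring ends at EOS.
- Section 10.4.8 does not. It says "If possible, AEs will be followed until resolved", which concerns events already recorded and not new onsets after EOS.
- The 12-weekly follow-up does not. It is prescribed for disease status and carries no AE recording of its own. It does give sites a planned occasion to learn of such an event, for patients who stopped without progression.
- Section 10.5.2 is the only candidate. Its wording covers every SAE without limit of time, but section 10.3 is the specific rule for the period after EOS. The two conflict, and the protocol does not say which prevails.

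**Step 3. Consider the size.** The protocol gives no rate of serious related events after EOS and does not reproduce the Brochure's list, so the number lost cannot be computed. Two statements suggest that it is small at present. Section 4.4.2 reports no treatment-related SAEs in the healthy-volunteer and psoriasis experience. Section 4.4.1 reports mostly grade 1 or 2 related events in this trial as of August 2015, with some grade 3 (neutropenia, anemia, arthritis), no grade 4 and no deaths. On that record many late related SAEs would be new or more severe, and so would be SUSARs.

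**The case against.** The strongest reply is that the gap is narrow. Active collection of all AEs runs to 30 to 35 days after the last dose. Events recorded by then are followed until resolved where possible. The more-severe and more-specific tests bring many listed events back into the SUSAR definition. Dose escalation and the MTD rest on the first 4 weeks of treatment (sections 6.3.2 and 6.3.3) and are untouched. Because post-EOS surveillance is passive, late reports would not give a reliable incidence under any recording rule. All of this stands, and it limits the weight of the point. It does not remove the gap in the last row of the table or the mismatch with section 10.5.2.

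A reader might also infer stronger claims that the protocol does not support:

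- **That the animal data show late toxicity in this window.** Section 6.5.4 says "Alterations in serum complement in these animals were noted in the weeks to months preceding their unscheduled deaths". Those animals died or were sacrificed during a 39-week chronic toxicity study. The passage does not describe onset a month or more after dosing stopped, and it says that similar direct complement activation has not been observed in humans. The thrombocytopenia in section 6.5.5 is timed from the start of treatment with another oligonucleotide and linked to duration of exposure, not to stopping.
- **That one late case, once added to the Brochure, would stop the recording of all later ones.** The protocol does not say what the Brochure lists or when it is updated. A later case that was more severe or more specific would still be recorded.
- **That sites continue to see all patients.** The 12-weekly follow-up covers only those who stopped for reasons other than progression, and it ends at the limits in section 6.10.2.2.

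**Conclusion.** The point holds in a limited form. After EOS, a related or possibly related SAE that matches the Brochure in kind, severity and specificity is not recorded under section 10.3, even when the Investigator knows of it. Section 10.5.2 can be read to the contrary, and the two need reconciling. The group affected is probably small and its size cannot be calculated from the protocol, so no numerical estimate is offered. Sample size, power and the escalation rules are unaffected.

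The reason to act is that the omission is selective in the data for the primary objective and is cheap to remove. The severity is minor to moderate. The conclusion rests on reading section 10.3 as the specific rule for the period after EOS. If section 10.5.2 were meant to govern, the fault would be a contradiction between the two sections and not a loss of data.

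**What to change.** In section 10.3, replace the SUSAR restriction for the period after EOS with wording such as: *only SAEs judged related or possibly related to study drug, whether expected or not, will be recorded*. Add to section 10.5.2 that after EOS the notification duty applies to the same set of events. Keep post-EOS surveillance passive, and leave expectedness to decide expedited reporting under section 10.5.4, which needs no change.

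The cost is one sentence in section 10.3, an aligning phrase in section 10.5.2, and probably a few extra SAE forms. No visit, test or treatment rule changes. Because surveillance remains passive, the change does not turn late reports into incidence estimates. It only ensures that the related SAEs of which sites become aware are kept on the same basis, whether or not the Brochure already lists them.

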### 10.4. Characterizing Adverse Events

For each AE recorded the following characteristics will be noted.

#### 10.4.1. *Description of Event*

The diagnosis or description will be as specific and complete as possible (i.e., “lower extremity edema,” rather than just “edema”). Whenever possible, signs and symptoms due to a common etiology will be reported as an integrated diagnosis; for example, cough, runny nose, sneezing, sore throat and head congestion would be reported as “upper respiratory infection.”

#### 10.4.2. *Date and Time of Onset*

The date and time at which the event was first apparent. [Table-13](#) summarizes the basis for reporting the date and time of onset for the different types of AEs.

**Table-13. Reporting the Date and Time of Onset of adverse events for Different Types of Events**

Type of Event	Examples	Source of Date and Time of Onset
Symptom	Headache, feverish, paresthesiae	When first experienced by the patient
Sign (Finding)	Elevated blood pressure, enlarged liver on physical exam	When first observed by the Investigator or other study staff
Laboratory/ diagnostic result	Neutropenia, hyperglycemia, lesions on brain scan	When lab sample was obtained or diagnostic study performed

The time of onset of symptoms may be appreciably earlier than the date and time the Investigator becomes aware of the event. Some events may be apparent to the patient and Investigator independently, and information from each may contribute to the final report. For example, a patient may report the onset of a rash 2 days before being seen by a physician who makes a diagnosis of herpes zoster based on appearance and laboratory confirmation. In that case, there

is a single AE, with the date of onset based on the date of the initial observation by the patient and a specific description (herpes zoster) based on the clinical exam and tests.

#### **10.4.3. Relationship to Study Drug**

This determination is based on the Investigator's clinical judgment regarding the likelihood that the study drug caused the AE and may include consideration of some or all of the following factors:

- Alternative possible causes of the AE, including the patient's underlying disease or co-morbid conditions, other drugs, other host and environmental factors.
- Temporal sequence between the exposure to study drug and the AE.
- Whether the clinical or laboratory manifestations of the AE are consistent with known actions or toxicity of the study drug.
- Whether the AE resolved or improved with decreasing the dose or stopping the study drug (i.e., dechallenge); or recurred or worsened with re-exposure to the drug (i.e., rechallenge).

The relationship between the study drug and the AE will be described using one of the following categories:

- **Related** — the study drug is more likely the cause of the AE than other factors;
- **Possibly related** — there is a *reasonable* possibility that the study drug is the cause of the AE, including that the study drug and another factor(s) are equally likely as causes of the AE;
- **Unlikely related** — another factor is considered more likely the cause of the AE than the study drug;
- **Not related** — another factor is considered to be the cause of the AE.

Related and possibly related AEs may result during the use of the study drug as planned (per protocol), or from abuse, withdrawal or over-dosage of the agent.

#### **10.4.4. Severity**

The severity of clinical AEs (i.e., symptoms reported by the patient and/or signs observed by the Investigator) will be assessed using the guidelines summarized in [Table-14](#) [27].

**Table-14. Estimating Severity Grade**

Grade 1/Mild	Asymptomatic or mild symptoms; clinical or diagnostic observations only; intervention not indicated
Grade 2/Moderate	Minimal, local, or noninvasive intervention indicated; limiting age-appropriate instrumental activities of daily living a
Grade 3/Severe	Severe or medically significant but not immediately life-threatening; hospitalization or prolongation of hospitalization indicated; disabling; limiting self-care activities of daily living b
Grade 4/Life-threatening	Life-threatening consequences; urgent intervention indicated
Grade 5/Death	Death related to adverse event

a. Instrumental activities of daily living refer to preparing meals, shopping for groceries or clothes, using the telephone, managing money, ect.  
b. Self-care activities of daily living refer to bathing, dressing and undressing, feeding self, using the toilet, taking medications, and not bedridden.

#### **10.4.5. Grading of Laboratory Safety Tests for Reporting and Analysis**

Treatment-emergent abnormal laboratory results will be handled as follows:

- Graded using NCI-CTCAE Version 4.03 criteria
- Assessed as potential DLT events based on pre-specified criteria (see [Section 6.3.1](#))
- Reported as AEs when assessed as “clinically significant” using the procedures and criteria detailed in [Section 10.2](#).

#### **10.4.6. Management of Study Drug upon Occurrence of an Adverse Event**

For each AE the Investigator will indicate which one of the following actions regarding the administration of study drug was taken because of that AE:

- **Discontinued (withdrawn)** — study drug was stopped permanently due to the AE.
- **Dosing Interrupted** — study drug regimen was modified by being temporarily halted, i.e., 1 or more doses were not administered, but drug was not stopped permanently.
- **Dose Decreased** — study drug regimen was modified by subtraction, i.e., by decreasing the frequency, strength or amount.
- **None** — no change in the administration of study mediation.

For patients whose treatment is paused and then resumed at a lower dose level as detailed in [Section 6.5.2](#), the management of study drug will be recorded as “Dose Decreased.”

#### **10.4.7. Actions Taken for Management of AE**

Adverse events will be followed and managed by the Investigator, including obtaining any supplemental studies needed to define the nature and/or cause of the event (e.g., laboratory tests, diagnostic procedures, consultation with other health care professionals).

For each AE the Investigator will categorize as follows the actions taken to manage the AE:

- **Concomitant medication** — 1 or more medications (prescription or over-the-counter) were started or increased in dose; non-medication actions may *also* have been ordered.
- **Other action** — *only* non-medication action(s) were ordered as management of the AE (e.g., bed placed in Trendelenburg position, warm compresses applied to SC access site).
- **No action** — no actions were ordered for management of the AE.

